**Specific Aim 1:** To determine whether varenicline pharmacotherapy is enhanced by either a nicotine replacement adjuvant (i.e., patch NRT) or extended medication duration (i.e., 24 vs. 12 weeks postquit). The effects of these pharmacotherapy strategies will be reflected in main effects for both experimental factors, and in direct comparisons of the enhanced varenicline conditions with standard 12-week varenicline-only. The primary outcome will be 52-week biochemically confirmed smoking abstinence (7-day point-prevalence).

**Specific Aim 2:** To determine the effects of the varenicline conditions on additional critical outcomes such as 23-week point prevalence and prolonged abstinence, smoking cessation milestones (abstinence, latency to lapse, and lapse-relapse latency), cost-effectiveness, withdrawal severity, and adverse events. The variables that mediate and moderate (e.g., genotype) the effects of the different pharmacotherapies will also be identified.

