**Table 2. Schedule of Study Activities**

	Pre-Cessation	Treatment Phase						Phone Follow-up				
		V1	C1	V2	V3	C2	C3	C4	C5	C6 	C7	C8 
Week	Orientation	Wk - 2	-1	TQD	2	4	8	11	17	23	39	52
Screening & Informed consent	X											
Randomization	X											
Pre-cessation counseling		X	X									
Cessation counseling				X	X	X	X					
Exhaled CO	X	X		X	X					X 		X 
Short questionnaire on CO exposure	X	X		X	X					X 		X 
Smoking status	X	X	X	X	X	X	X	X	X	X	X	X
Blood sample for DNA/RNA and cotinine		X										
Non-cigarette nicotine use	X	X		X		X	X			X		X
Baseline questionnaires	X	X										
IVR assessments	X	X	X	X	X							
Treatment mechanisms assessment 		X	X	X	X	X	X	X	X	X	X	X
Medication provision		X		X			X					
Medication use assessment			X	X	X	X	X	X	X	X	X 	
Adverse events			X	X	X	X	X	X	X	X	X	X

If participants claim abstinence during this assessment call, they will be invited to an in-person visit to provide biochemical verification of abstinence (CO assessment).

Treatment mechanisms include withdrawal, affect, fatigue, cigarette liking/effects, stressors, cue exposure, motivation, and self-efficacy.

Timeline follow back only

week post-quit). Per our intention-to-treat data analysis plan, any randomized smoker who does not provide biochemically confirmed evidence of abstinence will be counted as a smoker; multiple imputation also will be performed in secondary analyses to further enhance scientific rigor. A daily smoking calendar will permit determination of lapse/relapse latencies for survival and milestones analyses. In order to enhance *scientific transparency*, we will post all assessment instruments and, ultimately, de-identified data, online (e.g., the UW-CTRI website; average of 7,000 hits/month over last year from 17,387 visitors), so that other researchers can use our de-identified data and instruments (see detail in Data Sharing Plan).

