the main and interactive effects of the two factors. Importantly, main effects obtained with dummy coding in 2-factor designs are directly interpretable even in the presence of a significant interaction as long as the interaction effect is included in the model. Thus, main effects will reflect the effects of V+P vs. V-alone, and the effects of 24- vs. 12-week treatment duration. Interaction effects would reveal whether the magnitude of differences in effects of the levels of V treatment varies in a multiplicative manner depending on duration. While we hypothesize that we will see only main effects in this research, interactions would be interpreted via visual inspection (the highest and lowest scores for the interacting treatment combinations should be readily apparent) and via simple effects tests. Second, we will conduct analyses typical of an RCT, which use logistic regression models with dummy coding to contrast each of the three enhanced varenicline treatments (12-week V+P, 24-week V-only and 24-week V+P) with the standard V-based treatment (12-week V-only). The V-only condition will serve as the reference condition because the intent is to determine if any of the enhanced V-based treatments is superior to that condition. Covariates will include sex, race, treatment site, and level of tobacco dependence (FTND item 1). Results will be reported with and without covariate adjustment and the specific effects of sex and race on each outcome will be explored. The same analytic approach will be used for secondary abstinence analyses (e.g., point-prevalence at 6-months and prolonged abstinence). The intent-to-treat principle with the assumption of missing-smoking will be used for abstinence analyses but will be supplemented with sensitivity analyses and multiple imputation for missing data to support scientific rigor. The latter models will assume that 80% of dropouts return to smoking and that abstinence likelihood is related to baseline smoker covariates. Analyses of secondary abstinence outcomes will support scientific rigor by controlling for experiment-wise error in families of related tests. Milestones analyses will be conducted as in our prior research. For instance, latency between initial abstinence and lapsing, and latency between lapsing and relapse, will be computed with Cox proportional hazards regression/survival models.

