**PROTOCOL**  
“Quitting Using Intensive Treatment Study (QUITS)”  
PI: [name] and [name] ; UW-CTRI Grant:

In terms of the effects of increased duration of medication use, Schnoll et al., found that 24 versus 8 weeks of nicotine patch increased abstinence rates by only about 5 percentage points at 52-week follow-up. However, extended V treatment (24 weeks total) increased abstinence rates at 52 weeks post-TQD by about 10 percentage points in one study just among patients who were abstinent early in treatment, and by about 40 percentage points in another, smaller study. We believe that extended medication will increase abstinence rates by 7-11 percentage points (with regard to the V-only and V+P conditions, respectively) because research shows that extended pharmacotherapy both reduces relapse in those who are abstinent and increases the likelihood of cessation amongst those who have lapsed. Moreover, both NRT and V produce such effects, thus, these actions could be additive in those using both active agents. Because of the possibility of an additive effect, we posit slightly higher increases in Duration-related abstinence rates for the V+P condition than for the V-only condition. However, the uncertainty about the effect of Duration highlights the innovativeness of this work; we know very little about the effects of extended V treatment and nothing about the effects of extended V+NRT treatment. While the abstinence rates forecast may seem high, we believe they are reasonable given that they reflect the effects of 3 pharmacotherapy elements or dimensions (varenicline therapy, 24 week duration, and an NRT adjuvant) all supported by evidence of efficacy. The predicted outcomes result from the reasonable assumption that these 3 components will produce at least additive effects.

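### Lapse-to-relapse latency can be compared between arms only among people who lapsed, so for the Adjuvant and V+P contrasts it is not a randomised comparison and should be labelled descriptive beside an all-randomised milestone analysis

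*Combined protocol and SAP*

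**What the plan says.** Specific Aim 2 sets out to determine what the varenicline conditions do to several secondary outcomes, among them "smoking cessation milestones (abstinence, latency to lapse, and lapse-relapse latency". The Cessation paragraph of the Analytic Approach gives the method by citation and example: "Milestones analyses will be conducted as in our prior research", and then, for instance, "latency between initial abstinence and lapsing, and latency between lapsing and relapse, will be computed with Cox proportional hazards regression/survival models". The data source is described under Smoking Outcome Measures, in the text after Table 2: "A daily smoking calendar will permit determination of lapse/relapse latencies for survival and milestones analyses". The protocol text defines neither lapse nor relapse.

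The intention-to-treat statement is limited in scope: "The intent-to-treat principle with the assumption of missing-smoking will be used for abstinence analyses". The four baseline covariates (sex, race, site and one dependence item) are listed with the abstinence models and not repeated for the milestones. Statistical control for smoking during the quit attempt is mentioned only under Mediation and Moderation. The milestones text does not say that lapsers are a selected group, does not call the analysis descriptive, and names no milestone comparison in everyone randomised.

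The power rationale below Table 4 expects treatment to act both before and after a lapse. It says that "research shows that extended pharmacotherapy both reduces relapse in those who are abstinent" and that it "increases the likelihood of cessation amongst those who have lapsed".

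**The concern.** Randomisation balances the arms at entry. It does not balance the subgroup who later lapse when treatment affects who lapses. If the patch prevents lapses mainly in people who are less prone to smoke, those who still lapse on the patch are on average harder cases than lapsers on placebo patch, and would be expected to relapse sooner even if the patch does nothing after a lapse. This is selection. It arises even when hazards are proportional, and baseline covariates remove only the part that they explain.

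Latency from initial abstinence to lapse has the same weakness if it is restricted to people who achieved abstinence. The Adjuvant arms already differ before that point, because patch treatment starts two weeks before the TQD.

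At stake is the interpretation of an Aim 2 result. A hazard ratio reported as a treatment effect on lapse-relapse latency could suggest post-lapse harm from the patch where there is none, or hide a real benefit.

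**Working it through.** The plan gives no event count, hazard ratio or power for the milestones, so there is no figure of its own to reproduce. The check asks how large the selection can be under stated assumptions.

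**Step 1: imbalance among lapsers, by formula.** Let proneness u follow a gamma distribution with mean 1 and variance v, and let it multiply the lapse hazard. If S is the proportion who have not lapsed by week 52, then

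mean proneness among lapsers = (1 − S^(1+v)) / (1 − S).

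Table 4 predicts 25.0% abstinent on 12-week V-only and 44.9% on 24-week V+P. Using non-abstinence (75% and 55.1%) as a stand-in for lapsing, which is an assumption:

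- v = 1, standard arm: (1 − .25²)/.75 = .9375/.75 = 1.25
- v = 1, V+P arm: (1 − .449²)/.551 = .798/.551 = 1.45
- v = 0.5, standard arm: (1 − .25^1.5)/.75 = .875/.75 = 1.17
- v = 0.5, V+P arm: (1 − .449^1.5)/.551 = .699/.551 = 1.27

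The V+P lapsers are the more prone group before any post-lapse effect.

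**Step 2: effect on the Cox hazard ratio.** Assumptions, none from the documents: lapse hazard .004 per day and relapse hazard .03 per day, both multiplied by the same lognormal proneness; 364 days; treatment multiplies the lapse hazard only. The true post-lapse hazard ratio is therefore 1.00. Rejection rates are two-sided at 5% with N = 1250, and ranges cover repeated runs.

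| Lapse HR | SD of log proneness | Apparent HR among lapsers | Rejection rate |
|---|---|---|---|
| any | essentially none | 1.00 | 4–5% |
| .8 | 0.5 | 1.01 | about 6% |
| .8 | 1.0 | 1.03 | 7–8% |
| .7 | 0.5 | 1.02 | about 6% |
| .7 | 1.0 | 1.05–1.06 | 10–12% |
| .6 | 1.5 | 1.11 | 28–30% |

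The first row shows that shared proneness drives the excess. An SD of 1.5 is extreme: the central 95% of people then span a factor of exp(2 × 1.96 × 1.5) = exp(5.88), about 350. At SD 0.5 the factor is exp(1.96), about 7.

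With a true post-lapse benefit (HR 0.90), the last three rows give 0.93, 0.98 and 1.04: attenuated, nearly erased, then reversed.

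**Step 3: a different proneness distribution.** Gamma proneness with v from 0.25 to 2, assumed 52-week lapse proportions from 75/55.1% to 95/90% (control/treated), and a median of 4 weeks from lapse to relapse in the control arm at u = 1 gave apparent hazard ratios of 1.02 to 1.29 with no post-lapse effect. These are larger partly because the implied lapse effects are stronger. For 75/55.1% at v = 1 the cumulative lapse hazards are 1/.25 − 1 = 3 and 1/.449 − 1 = 1.23, a ratio of .41. The result confirms the direction and does not serve as an estimate of size.

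**Step 4: Duration.** The Duration arms receive the same treatment until about week 12, and the IVR Assessments section expects most lapses within a reporting window that ends 14 days after the quit day. With the lapse effect confined to weeks 12–24, the apparent hazard ratio was 1.00–1.02 and rejection 4–7%.

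**Step 5: an all-randomised counterpart.** In the gamma model, time from quit day to relapse in everyone randomised (75/55.1%, 85/70% and 95/90% lapsing) gave hazard ratios of 0.58–0.92 with no post-lapse effect and 0.57–0.87 with a true post-lapse HR of 0.90. The direction was beneficial throughout. These figures mostly reflect prevented lapses and do not estimate the post-lapse effect. Everyone starts abstinent in this simulation, so the handling of never-abstinent participants was not tested.

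**The case against.** Several objections have force.

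- **The trial already has randomised comparisons.** Point-prevalence and prolonged abstinence at 23 and 52 weeks are analysed in everyone randomised, with missing counted as smoking. A reader might infer that the trial could declare the patch harmful overall. The documents do not support that, because one secondary milestone is exposed and the abstinence analyses are not.
- **The extended-medication rationale is barely exposed.** A reader might infer that selection undermines the test of whether longer treatment helps after a lapse. Step 4 shows almost no bias there. The rationale also speaks of renewed cessation after a lapse, which is a different outcome from latency to relapse.
- **Shorter remaining follow-up is not itself a bias.** People who lapse later have less time before week 52, but that is ordinary administrative censoring, which a Cox model accommodates. Only the selection on proneness matters.
- **Part of the method is unseen.** The Cox models are given as an example and the rest is deferred to cited work, so a safeguard there cannot be excluded. It would still have to appear in this plan to be prespecified here.
- **The replacement answers another question.** Time from quit day to relapse merges failure to quit, lapse and the course after a lapse, whereas Aim 2 wants these stages apart. This stands, and is why the conditional model should be kept.

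None of these restores randomisation to a comparison made among lapsers.

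**Conclusion.** The concern holds as a limited point on a secondary analysis. For the Adjuvant contrast and for either V+P arm against 12-week V-only, the lapser-only Cox model is not protected by randomisation and can be biased against the arm that prevents lapses. Abstinence-to-lapse latency shares the problem if it is confined to initial abstainers.

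The size rests on assumed lapse effects and shared proneness, which the documents do not give. It is close to nominal when shared proneness is weak, moderate (10–12% false positives) at lapse HR .7 and SD 1.0, and near 30% only when a strong lapse effect meets a very wide spread of proneness. It also shrinks if nearly everyone lapses in both arms: in the gamma model 95/90% lapsing gave 1.02–1.12. The bias is a possibility that the plan should guard against; the documents do not show that it will be large.

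**What to change.** In the Cessation paragraph of the Analytic Approach:

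1. Add a milestone comparison from the TQD in everyone randomised, and base statements about treatment effects on it. Either time from TQD to relapse, with those never abstinent counted as relapsed at day 0, or a multi-state model (abstinent, lapsed, recovered, relapsed) reporting the probability of each state over time by arm would serve. The multi-state version keeps more of the separation that Aim 2 wants.
2. Keep the lapse-to-relapse Cox model, adjusted for baseline dependence and time to lapse, and label it descriptive and not a randomised comparison. Apply the same label to abstinence-to-lapse latency if it is restricted to initial abstainers. The adjustment does not replace the label. In the gamma model, mean proneness at a given lapse time is (1 + v)/(1 + vΛ), where Λ is the cumulative lapse hazard to that time. An arm with a lower Λ therefore still has the more prone lapsers.
3. State the definitions of lapse and relapse and who is in each risk set, instead of relying on citation.

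The cost is plan wording and one extra model on the daily smoking calendar already collected. The downside is that a TQD-based time to relapse combines the milestones, so it supplements the conditional analysis and does not replace it.

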Building on our recent NHLBI-funded publication in *JAMA* that described the modest effectiveness of varenicline pharmacotherapy, the proposed research will use a factorial design to evaluate two different medication use strategies on their ability to markedly enhance varenicline effectiveness in a large cohort of current smokers. Smokers (N=1250) will be randomly assigned to one of two levels for each of two factors: 1) an Adjuvant factor (varenicline + placebo patch versus varenicline + nicotine patch), and 2) a Duration factor (12 versus 24 weeks of active medication). Thus, this factorial design yields a "standard" varenicline treatment (12 weeks of active varenicline and 12 weeks of placebo varenicline + 24 weeks of placebo patch), and 3 *enhanced* treatments: 1) 12 weeks of active varenicline and 12 weeks of placebo varenicline + 24 weeks of active patch, 2) 24-weeks of active varenicline + 24 weeks of placebo patch, and 3) 24 weeks of active varenicline + 24 weeks of active patch. Both treatment modifications, longer duration therapy and use of a nicotine replacement therapy (NRT) adjuvant, have produced some quite promising effects. However, in both cases these modifications have been little researched, their effects are not *consistently* positive, and they have not been implemented in a potentially optimal manner. We will implement each modification in an innovative manner designed to enhance its effectiveness. In addition, all participants will be given counseling that supports adherent medication use and that is readily translatable to healthcare settings. The scientific rigor of this work will be enhanced by the use of placebo medication, a large sample, and a factorial design. The latter will allow us to test both the main and interaction effects of the experimental factors. We will also be able to compare each enhanced treatment with standard 12-week varenicline-only therapy to determine whether any of these medication use strategies significantly enhances treatment effectiveness. Outcomes will include long-term smoking abstinence (52 weeks), cost-effectiveness, adverse events, and withdrawal severity. This design will allow us to evaluate two major pharmacotherapy strategies (an NRT adjuvant, extended duration) that yield four distinct varenicline-based treatments. Specific aims of this research are:

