**Note: Participants can withdraw their DNA consent by request to the study PI**

**IVR Assessments:** To enhance scientific rigor, participants will provide nightly data (via phone keypad responses to voice prompts or complete an on-line survey) for a total of 31 days (3 days prior to starting treatment, 14 days during pre-cessation treatment, 14 days post-target quit day; see Table 2). Each report will take about 3-4 minutes to complete. Reports will assess mood, anhedonia, withdrawal, cessation fatigue (post-quit), cue exposure and reactivity, and tobacco and medication use with brief items used in our prior successful research. Medication effects and reasons for not using medications will also be assessed. All reports will end with a reminder of the number participants can call to discuss any concerns they have about study medications. Nightly IVR data collection reduces error that might arise from memory decay and recall biases. This time frame should capture key pharmacotherapy effects, the peak of withdrawal, and most lapse occurrences. These assessments will capture potential treatment mechanisms/mediators, treatment effects, and variables related to safety/side effects. Our procedures entail minimal burden (~3-4 min/day) and yield high (~80%) completion rates. Those who report having difficulty maintaining a stable phone/email service will be provided phones to take IVR phone calls.

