**Table 3. Medication Dosing Regimens for the Factorial Experiment**

	Pre-Cessation Meds	Cessation Meds: 12 Weeks Duration	Cessation Meds: 24 Weeks Duration
Varenicline Pills	Days -7 to -5: 0.5 mg pill QD Days -4 to -1: 0.5 mg pill BID	Days 1 to Week 11: 1 mg pill BID Weeks 12-23: placebo pill BID	Weeks 1 to 23: 1 mg pill BID
Active Patch	Days -14 to TQD: 14 mg patch 14 mg patch	Weeks 1 to 12: 14 mg patch Week 13-24: placebo patch	Weeks 1 to 24: 14 mg patch

Note: The timing and dose adjustments for active nicotine patch shown above will be matched with the placebo patch given to the V-only condition. Also, medications may be discontinued or doses may be reduced in the case of adverse events.

Participants will receive medications and use instructions at Visit 1 and 2 and following the Week 8 call (via the mail: Table 2). Participants will be given an information sheet with medication instructions and a number to call with questions or to report concerning side effects or toxicity. Adverse events will be assessed at each person-to-person study contact during the treatment phase. Medication use will be assessed during each study contact during the treatment phase.

**Counseling:** Participants will receive counseling based on our recent factorial research and on Guideline recommendations. Pre-cessation counseling will occur at Visit 1 and Call 1 (3- and 1-week pre-TQD: Table 2). Counseling in these sessions will include instructions for using the medications with a special focus on smoking reduction, clear smoking reduction goals, and behavioral training to facilitate smoking reduction. Recent research suggests the value of combining precessation medication and reduction counseling. Cessation counseling will occur during Visits 3 & 4 and Calls 2 & 3 (Table 2) and will provide support, inculcate coping skills, promote motivation for quitting, and provide clear instructions regarding proper medication use. The medication adherence training will include elements that yielded promising effects in our prior research (e.g., data-based feedback on medication use, problem solving regarding adherence challenges, and motivational intervention to support medication

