***Mediation and Moderation:*** Candidate mediators of cessation treatment effects, gathered from IVR and follow-up phone assessments will be: medication use and side effects, withdrawal symptoms (e.g., craving, negative affect, anhedonia), anticipatory pleasure from smoking, adverse events, nicotine reward, nicotine anticipation, and reports of cue-elicited urges. Treatment will be modeled both as main effects and as contrasts of particular Adjuvant X Duration combinations that differ significantly in abstinence rate from the standard V treatment condition at follow-up. Mediation will be tested using multiple indices including the joint significance test. Care will be taken to preserve mediator/outcome temporal priority and the occurrence of smoking during the quit attempt will be statistically controlled. Mediation models including multiple mediators will use methods developed for use with dynamic mediator assessments (maximum likelihood estimation using hierarchical linear modeling: HLM 5.04101). Both 23- and 52-week abstinence will be used as outcomes, which will be modeled via a weighted least squares approach in Mplus. The 23-week outcome may be more sensitive to treatment mediation than the 52-week outcome. We will attempt to characterize orthogonal routes to outcome change via use of multiple covariates and models of multiple mediation. In these models, the individual mediators revealed as strongest in univariable analyses will be included in multi-mediator models as per our prior research.

Analysis of moderators of abstinence outcomes will use both logistic regression with model-fitting techniques and regression tree analyses that reflect differential treatment responses in 23- and 52-week abstinence. The logistic regression and regression tree approaches are complementary since the former fits interactions in the entire sample whereas

PROTOCOL  
 "Quitting Using Intensive Treatment Study (QUITS)"  
 PI: [name] and [name] ; UW-CTRI Grant:

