The predicted data would strongly implicate the additive effects of both 24-week duration and the P adjuvant as being necessary to achieve a marked increase in abstinence over standard V-based therapy. Of course, we might discover instead that a single treatment modification or enhancement confers as much benefit as the combination of the two components (e.g., 24-week V-only produces as much benefit as 24-week V+P). This finding would be welcome to the extent that it means that exceptionally strong results are obtained with the use of only one treatment enhancement, which would save money and perhaps reduce adverse events and burden.

**Statistical Power:** We computed power (via SAS PROC POWER) for the abstinence outcomes in Table 4, assuming  $p < .05$  and two-tailed tests. Power is .88 for the main effect for Duration (n's=625), and .97 for the main effect of Varenicline (V+P vs. V: n's=625). Moreover, power is  $> .99$  for the key hypothesis that the 24-week V+P combination will be superior to 12-weeks of V-only (n's=312). The N used clearly provides some room for error if the predicted outcomes are too sanguine. For instance, we noted above that some data suggest that the increase in abstinence seen with extended medication might be as small as 7%. The proposed N (1250) would permit detection of a 7 point difference with power = .80. Thus, the N proposed would provide good power to detect the proposed effects, and even effects that are modestly weaker, but still of public health significance.

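### A single Cox hazard ratio for Duration averages in about 12 weeks of identical treatment, and IVR mediators end before the Duration arms differ

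*Combined protocol and SAP*

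**What the plan says.** Specific Aim 2 lists latency to lapse and lapse-to-relapse latency among the outcomes on which the varenicline conditions are compared. The Cessation paragraph of the Analytic Approach says that "latency between initial abstinence and lapsing, and latency between lapsing and relapse, will be computed with Cox proportional hazards regression/survival models". It describes no time-varying Duration term, landmark, delayed entry or check of proportional hazards.

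For the pill in the 12-week arm, Table 3 gives "Days 1 to Week 11: 1 mg pill BID Weeks 12-23: placebo pill BID"; the 24-week arm stays on active pill to Week 23. For the patch, Table 3 puts the switch to placebo at Week 13. The Pharmacotherapy text starts placebo in Week 13 for both products.

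On mediation the plan says "Candidate mediators of cessation treatment effects, gathered from IVR and follow-up phone assessments will be" and then lists medication use, withdrawal symptoms, cue-elicited urges and others. Treatment enters these models as main effects, so Duration is included. IVR reporting stops 14 days after the target quit day. Of that window the IVR paragraph says "This time frame should capture key pharmacotherapy effects, the peak of withdrawal", and it adds that most lapses should fall inside it. The Counseling paragraph likewise expects most relapse early in the attempt. Phone assessments are at Weeks 4, 8, 11, 17, 23, 39 and 52.

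**The concern.** Until the switch, the two Duration levels are the same treatment under blinding, so the true Duration hazard ratio for first lapse is 1. If extended medication works, the ratio departs from 1 only afterwards. A Cox model with one Duration coefficient reports an average over both periods, weighted by where the events fall, and the protocol itself expects most of them early. The reported ratio would then describe neither period and would understate what extended medication does while it is being given.

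The mediation analysis has a related problem. Craving or withdrawal in the first 14 days cannot be changed by a difference in medication that begins about ten weeks later. A finding that these measures do not mediate Duration would be fixed by the design, yet could be read as evidence about mechanism.

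**Working it through.** **The plan's own figure.** No power or event count is stated for milestones or mediation. The only stated Duration power is .88, for 52-week abstinence with 625 per level. The Table 4 marginals (29.5% v 38.5%, two-sided .05) give .92 with 625 per level; 550 per level gives .88. That mismatch is a separate matter and nothing below depends on it.

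**Method.** Let f be the share of lapses before Week 12, where the hazard ratio is 1, and h the hazard ratio afterwards. Approximately,

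- whole-period HR = h^(1 − f)
- power = Φ(|ln HR| × √D / 2 − 1.96), with D the number of events (the negligible opposite tail is ignored).

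An analysis from divergence uses h and only the later events.

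**Case 1: Table 4 as a proxy.** Assume that 29.5% and 38.5% are lapse-free at Week 52. Point prevalence is not lapse-free survival, so this is only a calibration. With N = 1250, D = 1250 × (1 − .34) = 825. The common lapse-free proportion at Week 12, S, is not in the documents and is varied.

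Worked row, S = .60:
- Early events 1250 × .40 = 500, so f = 500/825 = .61.
- h = ln(.385/.60) / ln(.295/.60) = (−.444)/(−.710) = .625.
- Whole-period HR = .625^.394 = .83; power = Φ(.185 × 28.72/2 − 1.96) = Φ(.70) = .76.
- From divergence: 325 events; power = Φ(.470 × 18.03/2 − 1.96) = Φ(2.28) = .99.

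| S at Week 12 | f | h after Week 12 | Whole-period HR | Power by formula (simulated) | Power from Week 12 |
|---|---|---|---|---|---|
| .80 | .30 | .73 | .81 | .87 (.87) | .96 |
| .70 | .45 | .69 | .82 | .82 (.83) | .97 |
| .60 | .61 | .63 | .83 | .76 (.72) | .99 |
| .50 | .76 | .50 | .84 | .69 (.67) | >.99 |
| .45 | .83 | .37 | .85 | .66 (.62) | >.99 |

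Simulations used 1,500 trials per row. Repeat runs stayed within about .80 to .86 for the hazard ratio and .60 to .89 for power. If hazards were proportional from the start, the same endpoints would give HR .78 and power .94.

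**Case 2: smaller late effects.** Assume 624 per level, h = .60, and lapse in the 12-week arm of either 50% by Week 12 rising to 65% by Week 52, or 70% rising to 80%.

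Effect lasting to Week 52:
- 50% to 65%: the 24-week arm is .50 × (.35/.50)^.60 = .404 lapse-free, a gain of 5.4 points. Events 1248 × (1 − .377) = 778, of which 624 are early (f = .80). HR = .60^.198 = .90; power .29 by formula, .28 simulated. From Week 12: 154 events, power .89.
- 70% to 80%: .30 × (.20/.30)^.60 = .235, a gain of 3.5 points. Events 976, of which 874 are early (f = .895). HR = .60^.105 = .95; power .13. From Week 12: 103 events, power .74.

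Effect in Weeks 12 to 24 only, with constant hazard after Week 12 in the 12-week arm: the window holds about 51 of 802 events (6.4%) or 35 of 992 (3.5%). HR = .60^.064 = .97 or .60^.035 = .98 (simulated .97 to .99), with power .06 to .07. The gain at Week 52 is 1.0 to 1.5 points, and the window analysed alone has power of only .33 to .45.

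**No effect.** Simulated rejection is about .05 for both the whole-period and the landmark analysis.

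**Mediation.** This needs no arithmetic. IVR ends on day 14 and the arms diverge at about Week 12. With identical blinded treatment throughout, the expected Duration difference on any IVR measure is zero. The same holds for the Week 4, 8 and 11 calls. The calls from Week 17 on can show a difference.

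**The case against.** Several counter-arguments have force.

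- The latencies run from initial abstinence and from lapse, not from the quit day. Someone who lapses after the switch is under different treatment from the start of the lapse-to-relapse clock, so a hazard ratio of 1 in the first 12 weeks does not carry over to that outcome. This stands; the argument applies cleanly only to first lapse.
- A reader might infer that a Duration effect cannot appear, or will be reported as a ratio near 1. The documents do not support that. Under Case 1 the whole-period model still has power of about .60 to .89. The near-null ratios come from effects worth 1.0 to 5.4 points at Week 52, whereas the plan predicts 7 to 11 points for Duration.
- With no Duration effect, proportional hazards between the Duration arms holds. The average ratio is also a legitimate intention-to-treat contrast of assigning 24 rather than 12 weeks. Both are true, which is why the whole-period model should still be reported.
- The milestone sentence is given as an example, allows other survival models and refers to earlier work. That leaves room for a better model, but none is specified.
- The mediators include phone measures after divergence, and the plan requires temporal priority. That rule orders mediator before outcome; it does not require the mediator to follow divergence. A null path from Duration to an IVR measure would be correct, but uninformative.

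**Conclusion.** The point holds for time to first lapse and for the early mediators. A real Duration effect is non-proportional by design, and the single hazard ratio understates the late effect. The loss runs from moderate (HR about .80 to .86, power about .60 to .89, against .96 or more from divergence, with Table 4 as a proxy) to severe (HR .90 to .99, power .06 to .28, for the smaller late effects of Case 2). Which applies depends on the share of lapses before Week 12 and the size of the late effect. The documents quantify neither, so every power figure here rests on stated assumptions. The direction does not.

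The reach is limited. A reader might infer that the trial's main Duration test is compromised; it is not, because the 52- and 23-week abstinence comparisons use logistic regression and are untouched. There is no inflation of false positives. That IVR measures cannot carry a Duration effect follows from the schedule alone.

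**What to change.** - **First lapse.** For Duration, pre-specify a time-varying effect in study time: no difference before the arms diverge, estimated afterwards. Alternatively, use a landmark at divergence among those still lapse-free, who remain comparable because treatment was identical and blinded until then. Report the whole-period model as well, and keep the existing model for the Adjuvant factor.
- **Lapse to relapse.** Code Duration as a time-dependent effect by study week rather than a Week-12 landmark, which would drop those who first lapse after the switch. Interpret it with caution, because entry after divergence depends on a lapse that Duration may affect.
- **Mediation.** For Duration, use only measures taken after divergence and before the outcome: Week 17 for 23-week abstinence; Weeks 17, 23 and 39 for 52-week abstinence. A Week 23 measure coincides with the 23-week outcome. Use IVR mediators for the Adjuvant factor and contrasts that include it, not for 24-week against 12-week varenicline alone.
- **Divergence point.** Reconcile the Week 12 pill switch in Table 3 with Week 13 in the Pharmacotherapy text and the Table 3 patch row, so that the time at which the effect starts is defined.

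The cost is SAP wording and a few lines of code; the daily smoking calendar already supplies the dates. The downside is slightly more analysis and a smaller set for the landmark model.
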